## **11. STATISTICAL MEASUREMENTS, EVALUATIONS AND ANALYTICAL METHODS**

### **11.1. Assessment of Efficacy**

Monthly total seizure rates will be calculated for the entire open-label part of Study VRX-RET-E22-304 and described statistically. Monthly total seizure rates observed during the open-label extension period will be compared to the monthly total seizure rates observed during the Baseline phase of the double-blind study VRX-RET-E22-302. The percent change in monthly total seizure rates from the Baseline phase will be classified into <0, [0, 25), [25, 50), [50, 75), [75, 100] and described. The responder rate during the open-label study (defined as a reduction in seizure frequency  $\geq 50\%$ ) will also be summarized using descriptive statistics.

The number of seizure free days, in percent to the individual duration of the open-label treatment, will be calculated and summarized using descriptive statistics. This percentage will be classified into [0, 25), [25, 50), [50, 75), [75, 95), [95, 100), [=100] and described statistically.

All-cause withdrawal rates will be calculated as a percentage and respective "times to event" will be described by a Kaplan-Meier survival curve. Specific reasons for withdrawal will also be described separately.

This is an open-label extension study with the emphasis on safety. Efficacy is not the primary objective of this study unlike the double-blind study VRX-RET-E22-302. Descriptive statistics of efficacy measures such as number of patients, mean, standard deviation, median, minimum and maximum will be provided for continuous variables. The number and percentages in each category will be presented for categorical data. The pairwise t-test will be used to assess whether the retigabine treatment remains effective in the open-label extension study if necessary. The pairwise t-test may be sorted by the geographic region [Central/Eastern Europe vs. Rest of World (ROW)]. The safety assessments will use essentially the same descriptive statistics and pairwise t-test as mentioned above for efficacy. The complete details of efficacy analyses will be described in the Statistical Analysis Plan.

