#### 4.4 Efficacy Evaluation

“Monthly total partial seizure” as well as “monthly total seizure” rates will be calculated for the entire open-label part of Study VRX-RET-E22-304 and statistically described. “Monthly total partial seizure” rate is defined as the sum of total partial seizures throughout the open-label portion (of Study VRX-RET-E22-304), divided by open-label duration in days, standardized by 28 days (1 month). “Monthly total seizure” rate is defined as the sum of partial and generalized (or unclassified) seizures throughout the open-label duration in days, standardized by 28 days (1 month).

Monthly total partial seizure rates observed during the open-label extension period will be compared to the monthly total seizure rates observed during the Baseline phase of the double-blind study VRX-RET-E22-302. The baseline monthly total seizure rates will only be derived for patients who enter this open-label extension and have a monthly total partial seizure rate during the open-label extension period. The percent change in monthly total partial seizure rates from the Baseline phase will be classified into <0, [0, 25), [25, 50), [50, 75), [75, 100] with a description of the frequencies. The responder rate during the open-label study (defined as a reduction in seizure frequency  $\geq 50\%$ ) will also be summarized using descriptive statistics.

The monthly total partial seizure rates compared to the baseline monthly total partial seizure rate will be presented cumulatively for each timepoint (months 1, 3, 6, 9, 12, 16, 20, 24, 28, 32 and 36) during the open label extension period and separately for eleven cohorts of patients treated with retigabine for at least 1, 3, 6, 9, 12, 16, 20, 24, 28, 32 and 36 months. In each cohort, patients will be followed for entire indicated duration of treatment. For example, patients in the 36-month cohort will also be part of the shorter-duration cohorts.

A similar analysis will be repeated for the responder rate during the open-label study.

A plot of the median percent reduction from baseline in seizure frequency over time by duration of treatment will also be produced.

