FOOTNOTE: [1] BASELINE PHASE IN STUDY VRX-RET-E22-302

47

CONFIDENTIAL

RM2009/00475/00  
VRX-RET-E22-304

---

Program Path/sas program name

Run Date:

---

Filename: 87272\_304\_SAP\_v2\_final

page 46 of 148

Valeant Pharmaceuticals North America  
Protocol Number: VRX-RET-E22-304

PAGE X OF X

Use Template for TABLE 9.2 to produce:

TABLE 9.3 PERCENTAGE CHANGE IN MONTHLY TOTAL PARTIAL SEIZURE FREQUENCY FOR PATIENTS TREATED WITH RETIGABINE FOR AT LEAST 6 MONTHS DURING THE OPEN-LABEL EXTENSION  
TABLE 9.4 PERCENTAGE CHANGE IN MONTHLY TOTAL PARTIAL SEIZURE FREQUENCY FOR PATIENTS TREATED WITH RETIGABINE FOR AT LEAST 9 MONTHS DURING THE OPEN-LABEL EXTENSION  
TABLE 9.5 PERCENTAGE CHANGE IN MONTHLY TOTAL PARTIAL SEIZURE FREQUENCY FOR PATIENTS TREATED WITH RETIGABINE FOR AT LEAST 12 MONTHS DURING THE OPEN-LABEL EXTENSION  
TABLE 9.6 PERCENTAGE CHANGE IN MONTHLY TOTAL PARTIAL SEIZURE FREQUENCY FOR PATIENTS TREATED WITH RETIGABINE FOR AT LEAST 16 MONTHS DURING THE OPEN-LABEL EXTENSION  
TABLE 9.7 PERCENTAGE CHANGE IN MONTHLY TOTAL PARTIAL SEIZURE FREQUENCY FOR PATIENTS TREATED WITH RETIGABINE FOR AT LEAST 20 MONTHS DURING THE OPEN-LABEL EXTENSION  
TABLE 9.8 PERCENTAGE CHANGE IN MONTHLY TOTAL PARTIAL SEIZURE FREQUENCY FOR PATIENTS TREATED WITH RETIGABINE FOR AT LEAST 24 MONTHS DURING THE OPEN-LABEL EXTENSION  
TABLE 9.9 PERCENTAGE CHANGE IN MONTHLY TOTAL PARTIAL SEIZURE FREQUENCY FOR PATIENTS TREATED WITH RETIGABINE FOR AT LEAST 28 MONTHS DURING THE OPEN-LABEL EXTENSION  
TABLE 9.10 PERCENTAGE CHANGE IN MONTHLY TOTAL PARTIAL SEIZURE FREQUENCY FOR PATIENTS TREATED WITH RETIGABINE FOR AT LEAST 32 MONTHS DURING THE OPEN-LABEL EXTENSION  
TABLE 9.11 PERCENTAGE CHANGE IN MONTHLY TOTAL PARTIAL SEIZURE FREQUENCY FOR PATIENTS TREATED WITH RETIGABINE FOR AT LEAST 36 MONTHS DURING THE OPEN-LABEL EXTENSION

**PROGRAMMING NOTE: EVERY TIMEPOINT SHOULD BE INCLUDED WITHIN THE INDICATED DURATION OF OPEN-LABEL TREATMENT. E.G. MONTHS 1, 3, 6, 9, 12, 16, 20, 24, 28, 32 AND 36 WILL BE PRESENTED IN TABLE 9.11.**

48

CONFIDENTIAL

RM2009/00475/00  
VRX-RET-E22-304

Program Path/sas program name

Run Date:

Valeant Pharmaceuticals North America  
Protocol Number: VRX-RET-E22-304

PAGE X OF X

TABLE 10 RESPONDER RATE ( $\geq 50\%$  REDUCTION IN MONTHLY TOTAL PARTIAL SEIZURE FREQUENCY)  
SAFETY POPULATION

RESPONSE CATEGORY	RETIGABINE (N=XXX)
N	xx
RESPONDERS	xx (xx.x%)
NON-RESPONDERS	xx (xx.x%)

Valeant Pharmaceuticals North America  
Protocol Number: VRX-RET-E22-304

PAGE X OF X

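### SAP 4.4 plans only whole-period and cumulative seizure rates, so Tables 9.x and 11.x attenuate and delay any late loss of effect

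*SAP*

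**What the plan says.** SAP 4.4 gives one definition of the monthly total partial seizure rate. It "is defined as the sum of total partial seizures throughout the open-label portion", divided by open-label duration in days and scaled to 28 days.

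For results over time, the comparison with the Study 302 baseline "will be presented cumulatively for each timepoint" at Months 1, 3, 6, 9, 12, 16, 20, 24, 28, 32 and 36, and "separately for eleven cohorts of patients treated with retigabine for at least" 1 to 36 months. Membership within a cohort table is fixed: "In each cohort, patients will be followed for entire indicated duration of treatment". A programming note under the Table 9.x shells adds: "EVERY TIMEPOINT SHOULD BE INCLUDED WITHIN THE INDICATED DURATION OF OPEN-LABEL TREATMENT".

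For responders: "A similar analysis will be repeated for the responder rate during the open-label study". For Figure 1: "A plot of the median percent reduction from baseline in seizure frequency over time by duration of treatment will also be produced". That sentence does not say whether the plotted values are cumulative or by interval.

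The question these outputs serve is in Protocol 11.1: "whether the retigabine treatment remains effective in the open-label extension study". Long-term efficacy is also part of the secondary objective in both documents.

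**The concern.** A long-term extension is where one looks for waning of response. An average that runs from the start of the period to the timepoint carries all the good early months forward, so the later a loss occurs, the less it moves the reported figure. Responder status has the same weakness: a patient can keep it on past response alone.

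No other planned output isolates late efficacy. Tables 8, 10 and 12 use the whole-period rate, and the percentage of seizure-free days also pools the whole period. The rolling 6- and 12-month seizure-freedom measure counts a qualifying period wherever it falls, so it does not say when control was present. A report built from these tables could describe efficacy as largely maintained at Month 36 when control had been lost in the last months.

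**Working it through.** The documents state no figure to reproduce; sample size is declared not applicable and efficacy is descriptive.

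**Inputs**
- Timepoints, rate definition and cohorts: SAP 4.4.
- Illustrative reduction before loss, 48.3% (median), and illustrative responder rate, 46.4%: the earlier retigabine open-label extension described in Protocol 7.4. They are not predictions for this trial.
- Assumption: the Month t value is the average over Months 0 to t, and the reduction R is constant until Month L and zero afterwards.

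**Formulas**
- Cumulative reduction at Month t after the loss: C(t) = R × L / t.
- Interval reduction between t1 and t2: (t2 × C(t2) − t1 × C(t1)) / (t2 − t1).

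**Size of the dilution** (R = 48.3%)

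| Effect lost after | Month 28 | Month 32 | Month 36 | Every interval after the loss |
|---|---|---|---|---|
| Month 12 | 20.7% | 18.1% | 16.1% | 0% |
| Month 24 | 41.4% | 36.2% | 32.2% | 0% |
| Month 28 | 48.3% | 42.3% | 37.6% | 0% |
| Month 32 | 48.3% | 48.3% | 42.9% | 0% |

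For example, 48.3 × 32 / 36 = 42.9: a visible fall of 5.4 points where the true fall is 48.3 points. A loss after Month 12 is visible sooner: 48.3% at Month 12, then 36.2%, 29.0% and 24.1% at Months 16, 20 and 24.

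**Responder status.** A patient who loses all effect after Month L is still a responder at Month 36 if R × L / 36 ≥ 50%, that is R ≥ 50 × 36 / L.
- L = 32: R ≥ 56.25%.
- L = 28: R ≥ 64.3%.
- L = 24: R ≥ 75%. Check: 75 × 24 / 36 = 50.

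**Responder rate.** 200,000 patients were simulated with log-normal rate ratios and a median reduction of 48.3%. The SD of the log rate ratio is an assumption. The value 0.37 reproduces 46.4% responders: (ln 0.500 − ln 0.517) / z(0.464) = 0.37. The values 0.7 and 1.0 show the range. All patients lose all effect after Month L, so the true responder rate in every later interval is 0%.

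| SD | Before loss | Month 36, loss after 24 | Month 36, loss after 28 | Month 36, loss after 32 |
|---|---|---|---|---|
| 0.37 | 46.4% | 2.5% | 15.9% | 32.6% |
| 0.70 | 48.1% | 14.9% | 29.9% | 40.5% |
| 1.00 | 48.6% | 23.3% | 35.5% | 43.2% |

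**What can be recovered.** In a fixed cohort with equal follow-up, the interval mean follows from two cumulative means. With L = 32, (36 × 42.933 − 32 × 48.3) / 4 = 0, and the simulation agrees. Medians and responder rates cannot in general be recovered this way, because patients change at different times.

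**The case against.** - **Cumulative values still fall.** A reader might infer that the tables cannot show whether efficacy is maintained. The documents do not support that. Cohort membership is fixed and every timepoint is shown, so dropout does not distort the trend within a table, and an early or mid-study loss is plain. Dilution is severe only for loss in the last interval or two. This stands.
- **Interval means can be back-calculated** from Tables 9.x, apart from visit-window differences. This stands for means, but not for the medians in Figure 1 or the responder rates in Tables 11.x. Nor should a reader have to reconstruct the result.
- **The cumulative reading is an inference.** The SAP does not define the word, and the shell rows carry only month labels. The word could describe table layout. But the only defined rate is a whole-period one, which makes the running average the natural reading; if it was not meant, the SAP has no timepoint derivation at all. Either way the window must be stated.
- **The start of the window.** A reader might infer that it runs from first dose. SAP 4.4 speaks only of the open-label period, while SAP 4.3 sets Day 0 at the start of double-blind treatment. The start point is not given.
- **Figure 1.** A reader might infer that it has the same defect. The text does not call it cumulative, and the shell's drawing is not in the available text. What stands is that its rate is unspecified.
- **Efficacy is secondary and descriptive**, and loss of response also surfaces as withdrawal for unsatisfactory efficacy (Table 1) and time to discontinuation (Table 2). True, but those tables say nothing about seizure control in patients who remain.
- **Interval rates would not isolate retigabine**, because Protocol 9.7.1 and 9.9.1 allow background antiepileptic drugs to be changed and 9.7.1 allows new ones to be added. This stands and limits what the fix can claim.

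**Conclusion.** The point holds in a limited form. As planned, Tables 9.x and 11.x attenuate and delay a late loss of effect. With a 48.3% reduction lost completely, Month 36 would read 42.9% if the loss came after Month 32 and 32.2% if after Month 24, against a true interval value of 0%. The simulated Month 36 responder rate would be about 33% to 43%, or about 2% to 23%, in the same two cases.

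These sizes rest on the running-average reading, on abrupt and complete loss, on the earlier study's 48.3%, and, for responder rates, on an assumed SD of 0.37 to 1.0. Partial or gradual loss would give a different profile.

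It is a worthwhile and cheap improvement to a secondary, descriptive analysis. It does not invalidate the cumulative tables, and they need not be replaced.

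**What to change.** 1. State the cumulative window in SAP 4.4: start of open-label treatment to the timepoint.
2. Beside the cumulative values in Tables 9.x and 11.x, add an interval rate: partial seizures since the previous scheduled timepoint, divided by diary days in that interval, times 28. Report percent change and responder status against the Study 302 baseline partial-seizure rate.
3. Base Figure 1 on the interval rates, or show both and label them.
4. Add a note that interval results describe seizure control over time under changing background therapy, not the effect of retigabine alone.

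The cost is SAP wording, extra table columns and one derivation from the seizure dates in Listing 7. Interval values are noisier, chiefly for Months 0 to 1. With 30-day study months that interval has 30 diary days, against 56 in the 8-week baseline; it is the only interval shorter than baseline. From Month 12 each interval has about 4 × 30 = 120 days.

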Patients participating in Study 3065A1-205 were eligible for an open-label extension phase (Study 3065A1-212) if they experienced improvement in seizure control, did not experience adverse events that would prevent inclusion, and did not violate the double-blind study protocol. Patients who completed the interim (transition) phase of the double-blind portion of the study started with 300 mg TID, which could be increased weekly in increments of 150 mg/day, up to a maximum of 1200 mg daily. Concomitant AEDs could be adjusted to achieve the best efficacy/safety ratio. Patients who wished to discontinue retigabine during this open-label study entered a 3-week tapering period and a 10-day post-study follow-up period. Seizure frequency was recorded daily in a diary maintained by each patient. The efficacy of retigabine was evaluated by comparison of baseline seizure frequency (determined upon entry into the double-blind phase) with

seizure frequency during retigabine therapy in the extension study; this was calculated as a percentage change in total partial seizure frequency.

Of the 279 patients who completed Study 205, 222 enrolled in the open-label extension. The majority of these patients were white (213 or 95.9%) with a median age of 36 years. A total of 126 patients were male (56.8%) and 96 (43.2%) were female. The median duration of epilepsy at study entry was 20.7 years. Of these 222 patients, 18 (8%) discontinued within the first 3 months and 41 (18%) discontinued within 6 months. The most common cause for discontinuation was lack of efficacy. The most common daily dosage of retigabine was 900 mg (105 patients; 47.3%) and only a minority of the patients titrated the dosage to 1200 mg (53 patients; 23.9%). The median treatment duration during open-label extension phase was 358 days.

The median decrease in monthly total partial seizure frequency from baseline was 48.3%, which was similar to the results with the two highest retigabine dose groups (300 and 400 mg TID) in the randomized, double-blind phase. Patients assigned to the placebo group during the double-blind phase showed the largest seizure rate improvement during the extension phase. One hundred three patients (46.4%) showed a reduction in monthly total partial seizure frequency of 50%.

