#### 4.1.2 Analysis Populations

The Safety Population is defined as all patients who successfully completed the transition phase of Study VRX-RET-E22-302 and were enrolled into the long-term study VRX-RET-E22-304. The Transition phase is the phase of Study VRX-RET-E22-302 during which patients were adjusted to a 300 mg TID dose.

There will be no other population for this study.

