The number of seizure free days, in percent to the individual duration of the open-label treatment, will be calculated and summarized using descriptive statistics. “Percent seizure free days” is defined as the number of days without any seizures (partial or generalized) divided by open-label duration in days, in percent. This percentage will be classified into [0, 25), [25, 50), [50, 75), [75, 95), [95, 100), [=100] and described statistically. The most upper class represents completely seizure free patients, the next class almost seizure free patients.

Additionally, the proportion of subjects who become seizure free for 6 and 12 month rolling intervals will also be determined. That is, a subject who becomes seizure free for any 6 month period of time will qualify for the 6 month metric. A subject who becomes seizure free for any 12 month period of time will qualify for both the 6 month and 12 month metric.

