TABLE 11.10 RESPONDER RATE ( $\geq 50\%$  REDUCTION IN MONTHLY TOTAL PARTIAL SEIZURE FREQUENCY) FOR PATIENTS TREATED WITH RETIGABINE FOR AT LEAST 32 MONTHS DURING THE OPEN-LABEL EXTENSION  
TABLE 11.11 RESPONDER RATE ( $\geq 50\%$  REDUCTION IN MONTHLY TOTAL PARTIAL SEIZURE FREQUENCY) FOR PATIENTS TREATED WITH RETIGABINE FOR AT LEAST 36 MONTHS DURING THE OPEN-LABEL EXTENSION

**PROGRAMMING NOTE: EVERY TIMEPOINT SHOULD BE INCLUDED WITHIN THE INDICATED DURATION OF OPEN-LABEL TREATMENT. E.G. MONTHS 1, 3, 6, 9, 12, 16, 20, 24, 28, 32 AND 36 WILL BE PRESENTED IN TABLE 11.11.**

52

CONFIDENTIAL

RM2009/00475/00  
VRX-RET-E22-304

Program Path/sas program name

Run Date:

Valeant Pharmaceuticals North America  
Protocol Number: VRX-RET-E22-304

PAGE X OF X

TABLE 12 PROPORTION OF PATIENTS EXPERIENCING A REDUCTION IN MONTHLY TOTAL PARTIAL SEIZURE FREQUENCY  
SAFETY POPULATION

CATEGORY	RETIGABINE (N=XXX)
REDUCTION CATEGORY	
[-100%, -75%]	xx (xx.x%)
(- 75%, -50%]	xx (xx.x%)
(- 50%, -25%]	xx (xx.x%)
(- 25%, 0%)	xx (xx.x%)
WITHOUT REDUCTION	xx (xx.x%)

53

CONFIDENTIAL

RM2009/00475/00  
VRX-RET-E22-304

Program Path/sas program name

Run Date:

TABLE 13 PROPORTION OF SEIZURE-FREE DAYS  
SAFETY POPULATION

STATISTICS	RETIGABINE (N=XXX)
SEIZURE-FREE DAYS (%)	
N	xxx
MEAN	xxx.x
STD	xxx.xx
MEDIAN	xxx.x
MINIMUM	xxx
MAXIMUM	xxx
REDUCTION CATEGORY	
SEIZURE-FREE [=100%]	xx (xx.x%)
NOT SEIZURE-FREE	xx (xx.x%)
[95%, 100%]	xx (xx.x%)
[75%, 95%]	xx (xx.x%)
[50%, 75%]	xx (xx.x%)
[50%, 25%]	xx (xx.x%)
[0%, 25%]	xx (xx.x%)
NUMBER OF PATIENTS WHO WERE SEIZURE-FREE FOR	
6 MONTHS	xx (xx.x%)
12 MONTHS	xx (xx.x%)

54

CONFIDENTIAL

RM2009/00475/00  
VRX-RET-E22-304

TABLE 14 EXTENT OF EXPOSURE TO STUDY MEDICATION  
 SAFETY POPULATION

STATISTICS	RETIGABINE (N=XXX)
EXTENT OF EXPOSURE (DAYS)	
N	xxx
MEAN	xxx.x
STD	xxx.xx
MEDIAN	xxx.x
MINIMUM	xxx
MAXIMUM	xxx
RETIGABINE EXPOSURE CATEGORY (MONTHS)	
N	xxx (100.0%)
[0, 1]	xxx ( xx.x%)
(1, 3]	xxx ( xx.x%)
(3, 6]	xxx ( xx.x%)
(6, 9]	xxx ( xx.x%)
(9, 12]	xxx ( xx.x%)
(12,16]	xxx ( xx.x%)
(16,20]	xxx ( xx.x%)
(20,24]	xxx ( xx.x%)
(24,28]	xxx ( xx.x%)
(28,32]	xxx ( xx.x%)
(32,36]	xxx ( xx.x%)
>36	
DAILY DOSE OF RETIGABINE EXPOSURE (MG)	
N	xxx
MEAN	xxx.x
STD	xxx.xx
MEDIAN	xxx.x
MINIMUM	xxx
MAXIMUM	xxx

55

CONFIDENTIAL

RM2009/00475/00  
 VRX-RET-E22-304

TABLE 15 NUMBER (%) OF PATIENTS REPORTING TREATMENT-EMERGENT ADVERSE EVENTS  
 SAFETY POPULATION

SYSTEM ORGAN CLASS PREFERRED TERM	RETIGABINE (N=XXX)
ANY ADVERSE EVENT	xxx ( xx.x%)

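### Seizure freedom in Table 13 is a percent of each patient's own open-label time with no minimum stay, so short seizure-free stays count as complete seizure freedom, and the class described as almost seizure free allows up to 1.4 seizure days per 28

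*SAP*

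**What the plan says.** SAP 4.4 defines percent seizure-free days as a quantity that "is defined as the number of days without any seizures (partial or generalized) divided by open-label duration in days, in percent". It continues: "This percentage will be classified into [0, 25), [25, 50), [50, 75), [75, 95), [95, 100), [=100] and described statistically". The top two classes are then interpreted: "The most upper class represents completely seizure free patients, the next class almost seizure free patients". Protocol 11.1 uses the same denominator ("The number of seizure free days, in percent to the individual duration of the open-label treatment") and the same classes. The protocol synopsis adds the same interpretation of the top two.

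No minimum duration is attached. The only analysis population (SAP 4.1.2) is "all patients who successfully completed the transition phase of Study VRX-RET-E22-302 and were enrolled into the long-term study".

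SAP 4.4 then adds a fixed-length measure: "a subject who becomes seizure free for any 6 month period of time will qualify for the 6 month metric", with a parallel 12-month version. The Table 13 shell carries both, the rolling counts under the row heading "NUMBER OF PATIENTS WHO WERE SEIZURE-FREE FOR". In that shell the 95–100% row comes after a row for patients who are not seizure free. There is no baseline column, and the only denominator shown is the Safety Population N in the header.

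For percent change and responder rate, SAP 4.4 repeats the analysis in eleven cohorts defined by minimum treatment duration (Tables 9.1–9.11 and 11.1–11.11). The seizure-free-day classes get no such breakdown.

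**The concern.** The =100% class is easiest to reach with the shortest stay, because there are fewer days on which a seizure could occur. A row meant to show the best long-term outcome therefore mixes patients free of seizures for years with patients who left within days. The class below it is described in words that its lower boundary does not support. And without the same percentage at baseline, a reader cannot tell how much of the distribution was present before treatment, since most days are seizure free even in uncontrolled epilepsy.

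Long-term efficacy is a stated secondary objective (SAP 2). The SAP already controls for duration in its rate and responder analyses, so the absence here looks like an oversight rather than a choice.

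**Working it through.** The plan states no figure for this measure, so there is none to reproduce. The SAP rule is applied directly.

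**Inputs.** Rule and class limits: SAP 4.4. Study month of 30 days: protocol 10.1. Month of 28 days for seizure rates: SAP 4.4. Predecessor extension (protocol 7.4): 222 enrolled, 18 left within 3 months, 41 within 6 months, and "The median treatment duration during open-label extension phase was 358 days". Seizure rates of 1, 2 and 4 per 28 days are assumptions, because the documents give no baseline rate for this trial.

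**Rule.** Percent = 100 × (D − seizure days)/D, where D is the patient's open-label days.

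**The =100% class.**
- 7 days, no seizure: 7/7 = 100%, class =100.
- 7 days, one seizure day: 6/7 = 85.7%, class [75, 95).
- 36 months (36 × 30 = 1,080 days), one seizure day: 1,079/1,080 = 99.9%, class [95, 100).

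**The [95, 100) class.** The lower limit is one seizure day in 1/0.05 = 20. That is 28 × 0.05 = 1.4 per 28 days, or 365 × 0.05 = 18.25 a year. Several seizures on one day count once. A seizure exactly every 20 days sits on the edge:
- Over 365 days with the first on day 20, there are 18 seizure days: 347/365 = 95.07%, inside.
- With an early first seizure there are 19: 346/365 = 94.8%, outside.
- Every 21 days gives 95.2% (inside); every 19 days gives 94.7% (outside).

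**Baseline.** Four seizure days per 28 is 24/28 = 85.7%; two per 28 is 26/28 = 92.9%. Both fall in [75, 95), so the classes do not register that halving.

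**Chance of =100% by length of stay.** Assuming a Poisson process, P(no seizure in d days) = exp(−rate × d/28).

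| Rate per 28 days | 7 days | 14 days | 28 days |
|---|---|---|---|
| 2 | 61% | 37% | 13.5% |
| 4 | 37% | 13.5% | 1.8% |

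By 90 days it is 0.2% or less at both rates.

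**Net size.** Assume the 18 early leavers left uniformly over 90 days. The expected number classed =100% is 18 × 28/(90 × rate) × [1 − exp(−90 × rate/28)].
- Rate 4: 18 × 7/90 = 1.4 patients; 1.4/222 = 0.6%.
- Rate 2: 18 × 14/90 = 2.8 patients; 2.8/222 = 1.3%.
- Rate 1: 18 × 28/90 × (1 − 0.040) = 5.4 patients; 5.4/222 = 2.4%.

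The 41 − 18 = 23 who left in months 4 to 6 add at most 23 × 0.040 = 0.9 patients even at rate 1.

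**Rolling metrics.** A one-week patient cannot supply a 6-month interval, and a patient with a seizure every 20 days never has one. Both fail. Conversely, a patient with a seizure on day 1 and then 35 free months is outside the =100% row but meets both rolling metrics.

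**The case against.** The plan already contains a duration-robust measure. The rolling metrics are in the next paragraph of SAP 4.4 and in the same table, and neither problem case passes them. Table 13 does not print the phrase *almost seizure free*; it shows a numeric range placed after the not-seizure-free row. Comparison with baseline is carried by percent change (the primary efficacy variable) and responder rate: with one partial seizure per seizure day, the patient who halves from 4 to 2 is a responder in Table 10. The analysis is descriptive and efficacy is secondary. The net inflation is small. It may be smaller still if open-label duration includes the 3-week taper, which SAP 4.4 does not say: a day-7 leaver would then have about 7 + 21 = 28 days, and at 4 per 28 the chance falls from 37% to 1.8%.

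All of this stands as a limit on the harm. None of it removes the =100% row, adds duration to it, or changes the wording in SAP 4.4 and the synopsis.

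The objection is also right on two further matters. Counting early leavers as not reaching 6 or 12 months is conservative, so it is not a bias in the drug's favour. And a fixed 12-month minimum for the =100% class would be arbitrary: it would take the label from seizure-free late enrollees whose treatment ends for administrative reasons.

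**Conclusion.** The point holds as a correction to one table and one description. Followed exactly, the plan counts any short stay without a seizure as complete seizure freedom, and it describes up to 1.4 seizure days per 28 as almost seizure free. The expected inflation of the =100% row is about 1% of patients (0.6% to 1.3% at 4 and 2 seizures per 28 days; 2.4% at 1 per 28). That rests on predecessor dropout, Poisson seizures and uniform exit times. Lower on-treatment rates or earlier exits would raise it. The value for this trial cannot be computed from the documents.

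A reader might infer more, and the documents do not support it:
- *That the plan's seizure-freedom result as a whole is produced by short stay.* Only the own-time classes are exposed; the rolling metrics are not.
- *That every early leaver is counted as seizure free.* Only those with no seizure during their stay are.
- *That a patient with a seizure every 20 days is always in the second class.* That is the exact edge, and for some durations the timing of the first seizure decides it.
- *That about half of patients could not reach 12 months.* At 28 days per month, 12 months is 336 days, below the predecessor's 358-day median; at 30 days it is 360, just above. The SAP does not say which month length the rolling intervals use.

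**What to change.** In SAP 4.4 and Table 13:

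(a) Show the =100% row by open-label duration, using the month bands of Table 14 or the at-least-X-months cohorts of Tables 9 and 11, and name the 6- and 12-month rolling metrics as the seizure-freedom result. No fixed 12-month minimum is needed. Count the bands on open-label days: SAP 4.3 sets Day 0 at the start of Study 302 treatment. State the month length, and whether taper days count in open-label duration.

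(b) Drop the description of [95, 100) as almost seizure free, or express the class as seizure days per 28 days. Align the shell's brackets with the text; as drawn they overlap at 95%.

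(c) Add a column with the same percentage and classes from the 8-week Study 302 baseline diary.

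(d) Give the rolling metrics as a percent of all enrolled patients. SAP 4.3 bases percentages on patients with data at the relevant time point, which has no clear meaning for an any-interval metric. Show the percent of those treated at least 6 or 12 months only as a supplement, because it conditions on staying.

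Cost: some SAP wording and a few more rows and one column in one table, from diaries and dosing dates already held. The seizure-free figure will look less favourable.
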